6.1.2 Child recruitment

Following consent obtained by an educator, the research team will contact ECEC directors via phone (Appendix J) to advise of an educator participant at their centre and to seek support in identifying possible child participants who may meet the first two inclusion criteria specified below (i.e., correct age and no parental concerns regarding communication development). The research team will provide an email transcript (Appendix K) which centre directors will send to parents of potential child participants with the Parent Participant Information Sheet (Appendix L) and the Parent Consent Form (Appendix M) attached. If no responses are received from any

parents at the educator’s ECEC within 1 week, the research team will briefly call the director to follow up. If no responses are received from parents following this, the educator will be withdrawn from the study. In the event of between-stage child dropout, the Centre director will be asked to contact alternate potential child participants consistent with the initial child recruitment procedure.

[figure not shown]

Figure 3. Child recruitment. Relevant appendices are J, K, L and M

6.2 INCLUSION CRITERIA

Inclusion criteria will differ for educators and children who participate in this study. The inclusion criteria for each participant group are described below.

6.2.1 Educator inclusion criteria

Inclusion criteria for educators will include consent to participate in all stages of the study and anticipated completion of the Training program. No limitations on Educator participation will be made based on prior training or level of education. Routine early childhood educator training at both TAFE and University levels does not cover the content of the Training provided as

described for the current study. Group comparisons will be conducted at baseline to ensure homogeneity in group variability based on level of Education.

6.2.2 Child inclusion criteria

The inclusion criteria for child participants are: (1) aged 24-42 months and attend the consenting educator's ECEC at least one day per week, (2) no parental concerns about speech and/or language development, (3) no concerns identified based on the child's performance on the Communication section of the Ages and Stages Questionnaire (ASQ; Squires, Bricker & Twombly, 2009) (Appendix D) completed with a parent in an initial phone call, and (4) no concerns identified based on the Preschool Language Scales Screener (PLS; Zimmerman, Steiner, & Pond, 2011) (Appendix C) completed with a speech pathologist via videoconference at the child's ECEC. Eligibility will be confirmed after consent has been received from interested parents and the child's screening has been completed at the centre.

The ASQ screens children for concerns about overall development and can be a first step to identify children who require further evaluation for developmental concerns. It is a parent evaluation checklist that is suitable to screen the behaviour and functional communication development of children. Eligibility will also be determined based on children's performance on the PLS Screener, a direct screening assessment of language skills that is suitable to complete with children from birth to 8 years of age. The ASQ and PLS screener tools are both valid for the target sample of the current study. Parents of multilingual children will also be interviewed with questions from the BLEQ to establish the proportion of language exposure the child receives in all languages. The BLEQ will not be used to establish eligibility but will be used to gather information about the proportion of English and additional language exposure.

6.3 EXCLUSION CRITERIA

Exclusion criteria are only present for child participants in this study. Children will be excluded if: (1) their parent expresses concern about development based on the ASQ or, (2) the child does not pass the communication screening using the PLS Screener.

6.4 CONSENT

Written consent will be obtained from educators and a legal guardian of child participants (see Appendix I and M respectively). Consent will be provided directly to the research team or via centre directors; speech pathologists providing the training will not be aware of the consent process and will be initially blinded to educators and child participants. Assent will also be obtained from child participant at each stage of the research (including the initial language screening).

It is possible that the educators and/or caregivers of potential child participants will have English as a second or additional language. Due to this, the participant information and consent forms are written in simple English and all documentation provides contact information for the research team if the educator/caregiver wishes to ask questions about the research prior to participation. Also, given that consent is an opt-in process for the current study, we do not expect families who do not understand the documentation to provide consent.

7. PARTICIPANT SAFETY AND WITHDRAWAL

7.1 RISK MANAGEMENT AND SAFETY

While this research is considered low risk, no research can be considered absent of risk. Possible perceived risks for educators could include concerns about data being shared with their employer. This risk will be mitigated by advising all educators (via the participant information sheet) that no individual data will be shared with their employer. Only group data will be shared and individual participant will not be identifiable.

One possible risk for parents who provide consent for their child to participate in the study but who are subsequently withdrawn due to either (1) parental concern on the ASQ or, (2) the child failing the PLS-screener, may become distressed. Speech pathologists are well trained to support families who are faced with the possibility that their child has delayed communication development. All researchers on this team are experienced in supporting families and providing additional resources to assist families to seek further assessment if required.

Risks to children are minimal. Assent will also be obtained from child participants at each stage of the research (including the initial language screening). Child or educator distress when recording will be mitigated through delaying the recording until an alternative, more suitable time and discussion with the research team.

One final risk, which is present with any research or clinical activity conducted with children, is the disclosure of any event or activity that may relate to the protection and safety of the child involved. All members of the research team are qualified speech pathologists and mandatory reporters who are familiar with the procedures to report events that meet the child protection threshold of significant risk of harm. Caregivers are informed of the obligation of research staff to share information as required by law within the participant information sheet (page 3).

The principal investigator and a number of authors on this protocol have completed the Good Clinical Practice training. All named researchers will complete the Good Clinical Practice training before the commencement of data collection.

7.2 ADVERSE EVENT REPORTING

Any adverse events occurring during the course of this study will be reported to the appropriate authority. This may include Western Sydney Local Health District, the Sydney Children's Hospital Network Human Research Ethics Committee and/or the ECEC in which the data for the current study will be collected. A serious adverse event may include any breaches in data confidentiality or storage security. In the case of this event, the breach will be reported to WSLHD and SCHN HREC within 24 hours of the identification of this breach. Serious participant adverse events may include a child receiving an injury during the videoconference screening and/or video recording. Although the chance of these events are minimal due to the nature of the data collection, any incident observed by a member of the research team will be reported to the centre director immediately and to the relevant authority within the LHD within 24 hours.

7.3 HANDLING OF WITHDRAWALS

Educators who provide consent but for whom a suitable child pair cannot be identified will be withdrawn from the current study. Children will be withdrawn if they do not assent to any stage of data collection (after appropriate attempts to reschedule video recordings). Participating educators and the consenting guardian of participating children can withdraw their consent at any time

throughout the duration of this study. Data already collected from withdrawn participants may be included in descriptive analysis of the intended participant sample. Data from withdrawn participants will be removed from group-comparison analysis.

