5.6.2 Data collection schedule

Time 1. Following Educator consent, the Educator Demographic Questionnaire (see Appendix A) will be used to collect demographic information from educators during Time 1 via a Microsoft Teams survey or as a hard-copy. This survey requests the disclosure of information related to the educator’s age, gender, country of birth, languages spoken, language proficiency, work history, and education. Following parent consent, demographic information will be gathered

for child participants during Time 1 using questions from the routine demographic questionnaire of the LHD (see Appendix B). At least two other tasks will be conducted for child participants at Time 1. Firstly, the Preschool Language Scales Screener (PLS screener; Zimmerman, Steiner, & Pond, 2011) (Appendix C), a 10-minute screener to identify possible communication impairment, will be completed with the child by a member of the research team in their ECEC, with the Speech Pathologist administering the screener via videoconference due to the impacts of the pandemic. Second, the communication section of the Ages and Stages Questionnaire (ASQ; Squires, Bricker & Twombly, 2009) (Appendix D) will be completed with the child's parent via phone. For multilingual child participants, the BabyLabs Language Exposure Questionnaire (Cattani et al., 2014) (Appendix E) will be completed with the child's parent via phone (see Table 2).

Time 2-5. Fifteen-minute interactions within each educator-child dyad will be video recorded at these four time points. These interactions will take place at the ECEC they attend. Recordings will be viewed and coded by a named member of the research team for the purpose of analysis and outcome measures will be obtained (Appendix F). All interactions will be recorded in the ECEC attended by both the educator and the child. No home visits will be required for the current study. Furthermore, each educator will complete the routine educator Training Survey before and after their training period. That is, Group A will complete the survey at Times 2 and 3 and Group B will complete the questionnaire at Times 4 and 5.

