7.4 REPLACEMENTS

Educator and child participants may be replaced if they withdraw (or are withdrawn) between Stages of the research (either before Stage 1, or between Stage 1 and Stage 2). Participants will not be replaced if they withdraw within Stage 1 or Stage 2. Missing data will be removed pairwise in the event of within-stage dropout. In the event of considerable withdrawals and a compromised sample size, a second wave of data collection may be proposed (following HREC approval) to retain required sample size.

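### Section 7.3 turns one lasting refusal of a recording into study withdrawal and drops the child from every group comparison, so a late refusal can delete a complete Stage 1 change score

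*Protocol*

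**What the plan says.** Assent is sought repeatedly. Section 6.4 says: "Assent will also be obtained from child participant at each stage of the research (including the initial language screening". Section 7.1 repeats this. Section 5.6.2 sets the occasions: "Fifteen-minute interactions within each educator-child dyad will be video recorded at these four time points", namely Times 2, 3, 4 and 5.

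Section 7.3 gives the consequence of refusal: "Children will be withdrawn if they do not assent to any stage of data collection (after appropriate attempts to reschedule video recordings". On the data of anyone withdrawn it adds: "Data from withdrawn participants will be removed from group-comparison analysis". Data already collected may be used descriptively.

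Section 7.4 has a different rule for losses inside a stage: "Missing data will be removed pairwise in the event of within-stage dropout". It does not replace within-stage losses, but otherwise says: "Educator and child participants may be replaced if they withdraw (or are withdrawn) between Stages of the research", either before Stage 1 or between the two stages. Section 6.1.2 gives the route: "In the event of between-stage child dropout, the Centre director will be asked to contact alternate potential child participants".

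Sections 5.4 and 5.6.1 define Difference Score 1 as the change from Time 2 to Time 3 and Difference Score 2 as the change from Time 4 to Time 5. Section 8.2 makes the Stage 1 contrast primary. Section 8.1 sets 24 dyads, says that more are not feasible, and states a 10% dropout allowance.

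**The concern.** The children are 24 to 42 months old and are filmed four times. A refusal belongs to one occasion, and the guardian's consent still stands after it. Section 7.3 nevertheless treats a refusal that survives rescheduling as an exit from the study, and its last sentence applies that exit backwards. There are two consequences.

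- **Refusal at Time 4 or 5.** The child already has both Stage 1 videos. Once the child is withdrawn, that complete primary change score leaves the group comparison. A replacement child cannot restore it.
- **Refusal at Time 2 or 3.** The Stage 1 change score is lost under any rule. The child is then also not recorded at Times 4 and 5, although Difference Score 2 needs only those two videos. A replacement may fill the gap, but replacement is optional.

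The trial has 24 dyads and cannot enlarge, so complete pairs should not be discarded by a wording rule.

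**Working it through.** **1. The passages side by side.** For a child recorded at Times 2, 3 and 4 who lastingly refuses at Time 5:

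- Under 7.4, the missing value is removed pairwise. Difference Score 2 is lost and Difference Score 1 is kept.
- Under 7.3, the child is withdrawn and taken out of the group comparisons. Both scores are lost.

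Both rules apply to this child and give different primary analysis sets. The intention-to-treat statement in 8.2 does not settle it, because it concerns educators who drop out of the training.

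**2. The plan's own figure.** Inputs from 8.1: 12 dyads per group, two educators per centre, SD 0.3, ICC 0.1, alpha 0.05 (taken as two-sided), power 0.8.

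Design effect = 1 + (2 − 1) × 0.1 = 1.1.

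Detectable difference = (1.960 + 0.842) × 0.3 × √(2 × 1.1 / 12) = 0.360, against 0.358 stated.

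The stated figure therefore corresponds to all 24 dyads being analysed. At a 10% loss (24 × 0.9 = 21.6, or 10.8 per group) the same formula gives 0.379, and power at 0.358 is 75.3%.

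**3. Usable Stage 1 pairs.** Assumption: refusal after rescheduling has probability p at each of four recordings, independently, with no replacement and no other losses. As written, a Stage 1 pair survives only if all four recordings are assented to: 24(1 − p)^4. If a refusal counts only for its own stage: 24(1 − p)^2.

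| p | As written | Own stage only | Difference |
|---|---|---|---|
| 5% | 24 × 0.8145 = 19.5 | 24 × 0.9025 = 21.7 | 2.1 |
| 10% | 24 × 0.6561 = 15.7 | 24 × 0.81 = 19.4 | 3.7 |

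(Differences are taken before rounding.) With half of these dyads in each group, the formula in step 2 gives detectable differences of 0.399 against 0.379 at p = 5%, and 0.444 against 0.400 at p = 10%. The design effect is held at 1.1.

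If every Time 2 refusal is made good by a replacement before Stage 1, one factor drops out of each expression. At p = 5% the counts are 24 × 0.95^3 = 20.6 against 24 × 0.95 = 22.8. At p = 10% they are 24 × 0.9^3 = 17.5 against 24 × 0.9 = 21.6. The Stage 1 gap remains.

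**4. Usable Stage 2 pairs.** Before replacement the counts equal those in the table. If every refusal up to Time 4 is successfully replaced under the current wording, only Time 5 refusals count: 24 × 0.95 = 22.8 or 24 × 0.90 = 21.6. Both exceed the own-stage figures of 21.7 and 19.4. The Stage 2 gain therefore runs from the table's value down to none.

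**5. The 10% allowance.** Solving 1 − (1 − p)^k = 0.10 for k recordings that count:

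- k = 4 (all count, no replacement): p = 2.6%
- k = 3 (Time 2 refusals replaced): p = 3.5%
- k = 2 (one stage's pair only): p = 5.1%
- k = 1 (one irreplaceable recording): p = 10%

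**The case against.** The case on the other side is substantial, and much of it stands.

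- **The educator.** A reader might infer that one refusal ends recording for both members of the dyad. The text does not say so. Section 7.3 withdraws the child, and 6.1.2 and 7.4 let the educator go on with another child between stages. What remains is that replacement is optional. Section 5.6.1 places Times 3 and 4 in the five-week gap, yet Time 3 also completes the Stage 1 score, so it is unclear whether a refusal then counts as between-stage.
- **The trigger.** It is refusal after attempts to reschedule, not one missed video.
- **The threshold.** A reader might infer that the dropout allowance is exceeded at a very low refusal rate. The 2.6% figure needs all four recordings to count and no replacement. The supportable range is 2.6% to 10%, and the protocol gives no rate to place the trial within it.
- **Independence.** Refusals probably cluster within children. If the same children always refused, both rules would leave 24(1 − p) pairs and asking again would recover nothing.
- **Selective loss.** It is tempting to say that quieter children, or children of untrained educators, refuse more. Nothing in the protocol documents this, so it remains a possibility and not a finding.
- **Wording.** The sentence could mean refusal at every stage. The rescheduling clause points to individual recordings, and a sentence open to both readings needs rewording anyway.
- **Protection.** Ceasing to approach a child who keeps declining is defensible. It does not require deleting videos already made with assent.

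None of this answers the Stage 1 point. A pair completed before a Time 4 or 5 refusal is lost only through 7.3, and replacement cannot bring it back.

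**Conclusion.** The point holds in a limited form. Section 7.3 equates a refused recording with withdrawal and then removes the child from all group comparisons, in conflict with 7.4. The firm part is the avoidable loss of complete Stage 1 change scores after a Time 4 or 5 refusal. The weaker part is the loss of Stage 2 recordings after a Time 2 or 3 refusal, which depends on whether a replacement is sought and found.

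The avoidable Stage 1 loss is about 2 dyads of 24 at 5% refusal per recording and nearly 4 at 10%, given independent refusals and no replacement. It falls towards zero as refusals concentrate in the same children. These are illustrations and not forecasts. The documents do not support a claim that the rule stops both members of the dyad, that the dropout allowance will be breached, or that losses will differ by group. The change is still worth making, because the two sections cannot both be followed and the sample cannot be enlarged.

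**What to change.** Reword 7.3 to separate a refused recording from study withdrawal:

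- A recording not assented to after rescheduling is missing for that stage only.
- The dyad stays in the study and contributes to each stage for which it has both recordings, consistent with 7.4.
- Assent is sought again at the next scheduled time point, unless the guardian withdraws consent or asks for recordings to stop.
- The between-stage replacement option stays for children who are withdrawn.

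In 7.4, state whether a loss at Time 3 or Time 4 counts as within-stage or between-stage.

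The cost is a wording amendment and an ethics notification, with no visits beyond those scheduled. There are two small downsides. Staff may return for a child who declines again, and a child kept in the study may occupy a place that a willing replacement could have taken for Stage 2. The child's refusal is still respected on each occasion.

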8.2 STATISTICAL METHODS TO BE UNDERTAKEN

All questionnaire data will be collected via Microsoft Teams and exported in raw format for processing in R or SPSS. Demographic information (including age, languages spoken, language proficiency, educator level of education, educator years of experience, and child communication measures [ASQ and PLS]) will be described for all dyad participants. Two multiple linear regression analyses will be conducted to address the primary aim (Stage 1 contrast) and our secondary aim (Stage 2 contrast). The outcome (dependent variable) for both analyses will be children's mean length of utterance Difference Score across each Stage. Independent variables will be Group allocation (A or B) and cluster (ECEC). This analysis plan will allow for the primary investigation to be conducted on data collected in Stage 1. This primary analysis will investigate the impact of group allocation (Training [Group A]; Control [Group B]) and cluster (Educator Centre) on children's language output (Mean Length of Utterance). The secondary investigation will be conducted on data collected in Stage 2. This secondary analysis will investigate the impact of group allocation (No-training follow-up [Group A]; Training [Group B]) and cluster (Educator centre) on children's language output.

Intention-to-treat analysis will be completed in the event of educator drop-out from the training. If appropriate, per-protocol analysis will be completed to investigate the primary and secondary outcomes.

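### Section 7.3 drops withdrawn dyads from the group comparisons even after a completed stage, and is not reconciled with 7.4, with 8.2 or with replacement after allocation

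*Protocol*

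**What the plan says.** Section 7.3 of the protocol states the analysis rule: "Data from withdrawn participants will be removed from group-comparison analysis". The only use it keeps is descriptive: "Data already collected from withdrawn participants may be included in descriptive analysis of the intended participant sample". Withdrawal is not always the participant's own decision, since the study team also withdraws children: "Children will be withdrawn if they do not assent to any stage of data collection" (after attempts to reschedule).

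Section 7.4 gives a different rule for losses during a stage: "Missing data will be removed pairwise in the event of within-stage dropout". It also allows replacement: "Educator and child participants may be replaced if they withdraw (or are withdrawn) between Stages of the research", with the windows given as "either before Stage 1, or between Stage 1 and Stage 2". Section 6.1.2 repeats this for children: "In the event of between-stage child dropout, the Centre director will be asked to contact alternate potential child participants".

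Section 8.2 adds: "Intention-to-treat analysis will be completed in the event of educator drop-out from the training", with a per-protocol analysis as a possible extra.

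Three other sections matter here. Under 5.4 and 5.6.1, Difference Score 1 is the change from Time 2 to Time 3 and Difference Score 2 the change from Time 4 to Time 5. Under 8.2 the primary analysis uses Stage 1 and the secondary analysis Stage 2. Under 5.8, centres are randomised after educators and children have been recruited, and educators cannot be masked.

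**The concern.** The primary contrast needs only the Time 2 and Time 3 recordings. A rule that deletes a dyad for leaving after Time 3 discards a complete primary outcome because of a later event. Nothing in 7.3 shows that consent bars this use, since the same section allows those data to be described.

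Three sections then govern who is analysed (7.3, 7.4 and 8.2), and they do not agree. Where the text leaves a choice, it could be made once allocation and recordings are known. If those who leave differ in outcome from those who stay, deleting them can shift the group difference.

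Replacement raises a related problem. A dyad brought in after its centre's group is known was not part of the allocated set. In Group A, a new educator could be counted in the post-training follow-up although 7.4 does not explicitly require completion of Stage 1 Training.

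**Working it through.** **Step 1. Apply the rules to particular cases.**

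1. *A dyad completes Times 2 and 3, then withdraws between stages.* 7.3 removes it. The pairwise rule in 7.4 does not reach it, because that rule is limited to within-stage dropout. The intention-to-treat sentence in 8.2 does not reach it either, unless the educator dropped out of the Training. The complete Stage 1 score is lost to the primary contrast.
2. *A child completes Times 2 to 4 and does not assent at Time 5.* 7.3 withdraws the child and removes the data. Under 7.4 this is within-stage dropout, and pairwise removal, as usually understood, costs only the Stage 2 score. The two rules give different Stage 1 samples.
3. *An educator stops the workshops in Stage 1 but is still recorded at Time 3.* 8.2 keeps the dyad. If stopping the Training counts as withdrawal, 7.3 removes it. No definition settles this, and 7.4 uses withdrawal and dropout interchangeably.
4. *An educator or child is replaced between stages.* Randomisation has already taken place (5.8), so entry is after allocation. There is no Time 2 to Time 3 score, so only the secondary Stage 2 contrast is affected.
5. *An educator or child is replaced before Stage 1.* Entry may come before or after randomisation. If after, the primary contrast is affected.

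**Step 2. Size in dyads.** Section 8.1 plans 24 dyads, 12 per group. One complete dyad discarded is 1/24 = 4.2%. The 10% dropout in 8.1 is 0.10 × 24 = 2.4 dyads.

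**Step 3. Effect on precision.** Inputs from 8.1: SD of change 0.3, ICC 0.1, two educators per centre, alpha 0.05, power 0.8. Two-sided testing is assumed, as sidedness is not stated.

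- Design effect = 1 + (2 − 1) × 0.1 = 1.1.
- Detectable difference = (1.960 + 0.842) × 0.3 × √(2 × 1.1/n).
- n = 12 per group: 2.802 × 0.3 × √(2.2/12) = 0.360. The plan states 0.358, so its figure is reproduced closely, with all 12 dyads per group analysed.
- n = 10.8 per group (10% removed): 2.802 × 0.3 × √(2.2/10.8) = 0.379. Power at 0.358 falls from 79.6% to 75.3%.
- n = 10 per group: 0.394, with power 72.0% at 0.358.

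These losses are a ceiling on what 7.3 costs the primary contrast. A dyad lost before Time 3 has no Stage 1 score under any rule. Only dyads with both recordings can be recovered.

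**Step 4. Possible bias, as an illustration only.** Assume removal in one group only, depending on a normal variable that has correlation ρ with the change score. If a fraction q is removed, the group mean shifts by ρ × 0.3 × φ(z_q)/(1 − q), where z_q is the normal quantile at q and φ the normal density. For 2 of 12, φ(z_q) = 0.250, so with ρ = 1 the shift is 0.3 × 0.250/0.833 = 0.090.

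| Removed from one group | ρ = 0.25 | ρ = 1 |
|---|---|---|
| 1 of 12 | 0.013 | 0.050 |
| 2 of 12 | 0.022 | 0.090 |
| 3 of 12 | 0.032 | 0.127 |

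The comparison figure is the stated 0.358. If ρ = 0 the shift is zero. The sign depends on which group loses dyads and whether they are those with low or high change. The protocol gives neither ρ nor the split of withdrawals between groups.

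**The case against.** The strongest reply is that 7.3 and 8.2 concern different events. 8.2 speaks of dropping out of the Training and 7.3 of leaving the study. The protocol does treat the two as separable: under 5.6 and 6.1.1, educators who do not join the study still receive the Training. A reader might infer that 7.3 and 8.2 cannot both be followed. The text does not support that, because they can coexist once the two events are defined. What stands is that the protocol does not define them.

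A reader might also point to a child who declines at Time 5 as a certain loss of Stage 1 data. That overlooks the pairwise rule in 7.4, which would keep the Stage 1 score. That case shows a conflict between 7.3 and 7.4. The clear loss is the dyad that withdraws between stages, which 7.4 does not rescue.

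On replacement, one can say that 6.2.1 requires anticipated completion of the Training, that Group A is defined by training in Stage 1, and that replacement children come through the same recruitment procedure, with the research team screening for eligibility. This makes an untrained Group A replacement unlikely to be intended, but 7.4 does not exclude it explicitly. The objection is also right that between-stage replacements cannot alter the primary contrast.

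Finally, a reader might infer that removal favours the Training, since in Stage 1 only Group A carries the training burden. With 2 of 12 Group A dyads gaining nothing and the other 10 gaining 0.4, the full-group mean is (10 × 0.4 + 2 × 0)/12 = 0.333, against 0.40 after removal, a ratio of 1.20. The arithmetic is right but every input beyond the group size is assumed. Child non-assent and withdrawn consent can occur in either group, and for educators who leave the Training 8.2 already promises intention-to-treat.

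**Conclusion.** The point holds in a limited form. As written, 7.3 removes complete Stage 1 outcomes from the primary contrast when a dyad withdraws between stages, at 4.2% of the planned sample per dyad. It conflicts with 7.4 on within-stage dropout and is unreconciled with 8.2 for want of a definition. If all of the planned 10% were lost in this way, the detectable difference would rise from 0.360 to 0.379, assuming a two-sided normal approximation and the inputs of 8.1.

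Bias is possible, not established. It requires withdrawal to be related to outcome, and the protocol supports neither a direction nor a size. Between-stage replacement is a matter for the secondary Stage 2 contrast only. Replacement before Stage 1 could reach the primary contrast if it follows randomisation.

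A separate analysis plan might settle some of this. The protocol itself, however, already states these rules, and they need to agree.

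**What to change.** - **7.3:** Distinguish stopping the Training from withdrawing consent for data use. Replace the removal sentence with: *Every dyad with both recordings for a stage is analysed in that stage in its allocated group, whatever training was completed and whether or not it withdraws later, unless consent to use the data is withdrawn.*
- **7.4 and 8.2:** Align both with this sentence, so that within-stage dropout and dropping out of the Training follow one rule.
- **7.4 and 6.1.2:** State that dyads added after randomisation are left out of the main analyses and reported only in a supplementary analysis. In that analysis, count a Group A replacement as follow-up only if the educator completed Stage 1 Training.

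The cost is wording in four sections and a main Stage 2 analysis that may be a dyad or two smaller. The primary Stage 1 analysis keeps dyads that it would otherwise lose, unless a replacement made before Stage 1 came after randomisation and has to be left out.
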